9. STUDY CALENDAR

9.1.1 Non-Surgical Arm Study Calendar

Time point	Visit 1	Visit 2	Visit 3	Visit 4	Visit 5	Final visit
	Screening	Start RT Baseline	Halfway RT ~3.5 Weeks	End of RT ~7 Weeks	~3Months after RT	~6 Months after RT
Medical History	X					
Study Blood test		X	X	X	X	X
CT scan		X			X	
Pregnancy Test	X					

RT = radiotherapy

* Study visit are dependent on treatment events like start/end of pre- or post-op radiotherapy and surgery. Therefore treatment delay will result in delay of study visits.

CONFIDENTIAL

This document is confidential. Do not disclose or use except as authorized.

9.1.2 *Surgical Arm Study Calendar*

	Visit 1	Visit 2	Visit 3	Visit 4	Visit 5	Visit 6	Visit 7	Visit 8	Final Visit
	Before Surgery				Surgery Week		After post-op RT	Follow-Up	
	Screening	Start RT Baseline	End RT ~5.5 Weeks	3-5 days before surgery	Surgery stage 1	Surgery stage 2	End post-op RT	1 month after post-op RT	4 months after post-op RT
Medical History	X								
Eligibility blood test	X								
CT scan		X		X					
Study Blood test		X	X				X	X	X
Bone Biopsy					X	X			
Dispense drugs	X		X						
Pregnancy Test	X								

RT = radiotherapy

* Cycle 1 drugs will be taken between visit 1 and 2. Cycle 2 drugs will be taken between visit 3 and 4*
 Study visit are dependent on treatment events like start/end of pre- or post-op radiotherapy and surgery.
 Therefore treatment delay will result in delay of study visits.

10. MEASUREMENT OF EFFECT

N/A for this corellative study

11. ADVERSE EVENT REPORTING REQUIREMENTS

11.1 Definitions

11.1.1 *Adverse Event (AE)*

An adverse event (AE) is any undesirable sign, symptom or medical condition or experience that develops or worsens in severity after starting any study procedure specified in the protocol.

CONFIDENTIAL

This document is confidential. Do not disclose or use except as authorized.

Abnormal laboratory values or diagnostic test results constitute adverse events only if they induce clinical signs or symptoms or require treatment or further diagnostic tests.

11.1.2 *Serious adverse event (SAE)*

A serious adverse event (SAE) is any adverse event, occurring as a result of one of the study procedures:

- Results in death
- Is life-threatening. Life-threatening means that the person was at immediate risk of death from the reaction as it occurred, i.e., it does not include a reaction which hypothetically might have caused death had it occurred in a more severe form.
- Requires or prolongs inpatient hospitalization (i.e., the event required at least a 24-hour hospitalization or prolonged a hospitalization beyond the expected length of stay). Hospitalization admissions and/or surgical operations scheduled to occur during the study period, but planned prior to study entry are not considered SAEs if the illness or disease existed before the person was enrolled in the trial, provided that it did not deteriorate in an unexpected manner during the trial (e.g., surgery performed earlier than planned).
- Results in persistent or significant disability/incapacity. Disability is defined as a substantial disruption of a person's ability to conduct normal life functions.
- Is a congenital anomaly or birth defect; or
- Is an important medical event when, based upon appropriate medical judgment, it may jeopardize the participant and require medical or surgical intervention to prevent one of the outcomes listed above. Examples of such medical events include allergic bronchospasm requiring intensive treatment in an emergency room or at home; blood dyscrasias or convulsions that do not result in inpatient hospitalization, or the development of drug dependency or drug abuse.

Events **not** considered to be serious adverse events are hospitalizations for:

- routine treatment or monitoring of the studied indication, not associated with any deterioration in condition, or for elective procedures
- elective or pre-planned treatment for a pre-existing condition that did not worsen
- emergency outpatient treatment for an event not fulfilling the serious criteria outlined above and not resulting in inpatient admission
- respite care

11.1.3 *Expectedness*

Adverse events can be 'Expected' or 'Unexpected.'

11.1.3.1 Expected adverse event

Expected adverse events are those that have been previously identified as resulting from administration of the bone labeling drug. For the purposes of this

CONFIDENTIAL

This document is confidential. Do not disclose or use except as authorized.

study, an adverse event is considered expected when it appears in the current adverse event list, the Investigator's Brochure, the package insert or is included in the informed consent document as a potential risk.

Refer to Section 6.1 for a listing of expected adverse events associated with the bone labeling drugs.

11.1.3.2 Unexpected adverse event

For the purposes of this study, an adverse event is considered unexpected when it varies in nature, intensity or frequency from information provided in the current adverse event list, the Investigator's Brochure, the package insert or when it is not included in the informed consent document as a potential risk.

11.1.4 Attribution

Attribution is the relationship between an adverse event or serious adverse event and the study treatment. Attribution will be assigned as follows:

- Definite – The AE is clearly related to the study treatment.
- Probable – The AE is likely related to the study treatment.
- Possible – The AE may be related to the study treatment.
- Unlikely - The AE is doubtfully related to the study treatment.
- Unrelated - The AE is clearly NOT related to the study treatment.

11.2 Procedures for AE and SAE Recording and Reporting

Participating investigators will assess the occurrence of AEs and SAEs at all participant evaluation time points during the study.

All AEs and SAEs whether reported by the participant, discovered during questioning, directly observed, or detected by physical examination, laboratory test or other means, will be recorded in the participant's medical record and on the appropriate study-specific case report forms.

The descriptions and grading scales found in the revised NCI Common Terminology Criteria for Adverse Events (CTCAE) version 4.0 will be utilized for AE reporting. All appropriate treatment areas should have access to a copy of the CTCAE version 4.0.

A copy of the CTCAE version 4.0 can be downloaded from the CTEP website at:

http://ctep.cancer.gov/protocolDevelopment/electronic_applications/ctc.htm.

11.3 Reporting Requirements

For multi-site trials where a DF/HCC investigator is serving as the principal investigator, each participating investigator is required to abide by the reporting requirements set by the DF/HCC. The study must be conducted in compliance with FDA regulations, local safety reporting requirements, and reporting requirements of the principal investigator.

CONFIDENTIAL

This document is confidential. Do not disclose or use except as authorized.

Each investigative site will be responsible to report SAEs that occur at that institution to their respective IRB. It is the responsibility of each participating investigator to report serious adverse events to the study sponsor and/or others as described below.

11.4 Reporting to the Study Sponsor

11.4.1 *Serious Adverse Event Reporting*

All serious adverse events that occur after the initial dose of study treatment, during treatment, or within 30 days of the last dose of treatment must be reported to the DF/HCC Overall Principal Investigator on the local institutional SAE form. This includes events meeting the criteria outlined in Section 11.1.2, as well as the following:

- Grade 2 (moderate) and Grade 3 (severe) Events – Only events that are unexpected and possibly, probably or definitely related/associated with the intervention.
- All Grade 4 (life-threatening or disabling) Events – Unless expected AND specifically listed in the protocol as not requiring reporting.
- All Grade 5 (fatal) Events – When the participant is enrolled and actively participating in the trial OR when the event occurs within 30 days of the last study intervention.

Note: If the participant is in long term follow up, report the death at the time of continuing review.

Participating investigators must report each serious adverse event to the DF/HCC Overall Principal Investigator within 24 hours of learning of the occurrence. In the event that the participating investigator does not become aware of the serious adverse event immediately (e.g., participant sought treatment elsewhere), the participating investigator is to report the event within 24 hours after learning of it and document the time of his or her first awareness of the adverse event. Report serious adverse events by telephone, email or facsimile to:

[name].
Office [contact]
Email: [contact]
[contact]

Within the following 24-48 hours, the participating investigator must provide follow-up information on the serious adverse event. Follow-up information should describe whether the event has resolved or continues, if and how the event was treated, and whether the participant will continue or discontinue study participation.

11.4.2 *Non-Serious Adverse Event Reporting*

CONFIDENTIAL

This document is confidential. Do not disclose or use except as authorized.

Non-serious adverse events will be reported to the DF/HCC Overall Principal Investigator on the toxicity Case Report Forms.

11.5 Reporting to the Institutional Review Board (IRB)

Investigative sites within DF/HCC will report all serious adverse events directly to the DFCI Office for Human Research Studies (OHRS).

Other investigative sites should report serious adverse events to their respective IRB according to the local IRB's policies and procedures in reporting adverse events. A copy of the submitted institutional SAE form should be forwarded to:

[name].
Office [contact]
Email: [contact]
[contact]

The DF/HCC Principal Investigator will submit SAE reports from outside institutions to the DFCI Office for Human Research Studies (OHRS) according to DFCI IRB policies and procedures in reporting adverse events.

11.6 Reporting to the Food and Drug Administration (FDA) N/A

11.7 Reporting to the NIH Office of Biotechnology Activities (OBA) N/A

11.8 Reporting to the Institutional Biosafety Committee (IBC) N/A

11.9 Reporting to Hospital Risk Management

Participating investigators will report to their local Risk Management office any subject safety reports or sentinel events that require reporting according to institutional policy.

11.10 Monitoring of Adverse Events and Period of Observation

All adverse events, both serious and non-serious, and deaths that are encountered from initiation of study intervention, throughout the study, and within 30 days of the last study intervention should be followed to their resolution, or until the participating investigator assesses them as stable, or the participating investigator determines the event to be irreversible, or the participant is lost to follow-up. The presence and resolution of AEs and SAEs (with dates) should be documented on the appropriate case report form and recorded in the participant's medical record to facilitate source data verification.

For some SAEs, the study sponsor or designee may follow-up by telephone, fax, and/or monitoring visit to obtain additional case details deemed necessary to appropriately evaluate the SAE report (e.g., hospital discharge summary, consultant report, or autopsy report).

CONFIDENTIAL

This document is confidential. Do not disclose or use except as authorized.

Participants should be instructed to report any serious post-study event(s) that might reasonably be related to participation in this study. Participating investigators should notify the DF/HCC Overall Principal Investigator and their respective IRB of any unanticipated death or adverse event occurring after a participant has discontinued or terminated study participation that may reasonably be related to the study.

12. DATA AND SAFETY MONITORING

12.1 Data Reporting

12.1.1 Method

The QACT will collect, manage, and monitor data for this study.

12.1.2 Data Submission

The schedule for completion and submission of case report forms (paper or electronic) to the QACT is as follows:

Form	Submission Timeline
Eligibility Checklist	Complete prior to registration with QACT
On Study Form	Within 14 days of registration
Baseline Assessment Form	Within 14 days of registration
Treatment Form	Within 30 days of the last radiation treatment
Toxicity Report Form	Weekly during radiation treatment; Within 30 days of protocol defined follow up
Off Treatment/Off Study Form	Within 14 days of completing treatment or being taken off study for any reason
Follow up/Survival Form	Within 14 days of the protocol defined follow up visit date or call

12.2 Safety Meetings

The DF/HCC Data and Safety Monitoring Committee (DSMC) will review and monitor toxicity and accrual data from this trial as needed. The committee is composed of clinical specialists with experience in oncology and who have no direct relationship with the study. Information that raises any questions about participant safety will be addressed with the Principal Investigator and study team.

CONFIDENTIAL

This document is confidential. Do not disclose or use except as authorized.

The DSMC will meet as required to review toxicity and accrual data. Information to be provided to the committee may include: up-to-date participant accrual; current dose level information; DLT information; all grade 2 or higher unexpected adverse events that have been reported; summary of all deaths occurring within 30 days for Phase I or II protocols; for gene transfer protocols, summary of all deaths while being treated and during active follow-up; any response information; audit results, and a summary provided by the study team. Other information (e.g. scans, laboratory values) will be provided upon request.

12.3 Monitoring

Involvement in this study as a participating investigator implies acceptance of potential audits or inspections, including source data verification, by representatives designated by the Principal Investigator. The purpose of these audits or inspections is to examine study-related activities and documents to determine whether these activities were conducted and data were recorded, analyzed, and accurately reported in accordance with the protocol, institutional policy, Good Clinical Practice (GCP), and any applicable regulatory requirements.

All data will be monitored for timeliness of submission, completeness, and adherence to protocol requirements. Monitoring will begin at the time of participant registration and will continue during protocol performance and completion.

13. REGULATORY CONSIDERATIONS

13.1 Protocol Review and Amendments

This protocol, the proposed informed consent and all forms of participant information related to the study (e.g., advertisements used to recruit participants) and any other necessary documents must be submitted, reviewed and approved by a properly constituted IRB governing each study location.

Any changes made to the protocol must be submitted as amendments and must be approved by the IRB prior to implementation. Any changes in study conduct must be reported to the IRB. The DF/HCC Overall Principal Investigator (or Protocol Chair) will disseminate protocol amendment information to all participating investigators.

All decisions of the IRB concerning the conduct of the study must be made in writing.

13.2 Informed Consent

All participants must be provided a consent form describing this study and providing sufficient information for participants to make an informed decision about their participation in this study. The formal consent of a participant, using the IRB approved consent form, must be obtained before the participant is involved in any study-related procedure. The consent form must be signed and dated by the participant or the participant's legally authorized representative, and by the person obtaining the

CONFIDENTIAL

This document is confidential. Do not disclose or use except as authorized.

consent. The participant must be given a copy of the signed and dated consent document. The original signed copy of the consent document must be retained in the medical record or research file.

13.3 Ethics and Good Clinical Practice (GCP)

This study is to be conducted according to the following considerations, which represent good and sound research practice:

- E6 Good Clinical Practice: Consolidated Guidance www.fda.gov/downloads/RegulatoryInformation/Guidances/UCM129515.pdf
- US Code of Federal Regulations (CFR) governing clinical study conduct and ethical principles that have their origin in the Declaration of Helsinki
 - Title 21 Part 11 – Electronic Records; Electronic Signatures www.access.gpo.gov/nara/cfr/waisidx_02/21cfr11_02.html
 - Title 21 Part 50 – Protection of Human Subjects www.access.gpo.gov/nara/cfr/waisidx_02/21cfr50_02.html
 - Title 21 Part 54 – Financial Disclosure by Clinical Investigators www.access.gpo.gov/nara/cfr/waisidx_02/21cfr54_02.html
 - Title 21 Part 56 – Institutional Review Boards www.access.gpo.gov/nara/cfr/waisidx_02/21cfr56_02.html
 - Title 21 Part 312 – Investigational New Drug Application www.access.gpo.gov/nara/cfr/waisidx_02/21cfr312_02.html
- State laws
- DF/HCC research policies and procedures <http://www.dfhcc.harvard.edu/clinical-research-support/clinical-research-unit-cru/policies-and-procedures/>

It is understood that deviations from the protocol should be avoided, except when necessary to eliminate an immediate hazard to a research participant. In such case, the deviation must be reported to the IRB according to the local reporting policy.

13.4 Study Documentation

The investigator must prepare and maintain adequate and accurate case histories designed to record all observations and other data pertinent to the study for each research participant. This information enables the study to be fully documented and the study data to be subsequently verified.

Original source documents supporting entries in the case report forms include but are not limited to hospital records, clinical charts, laboratory and pharmacy records, recorded data from automated instruments, microfiches, photographic negatives, microfilm or magnetic media, and/or x-rays.

13.5 Records Retention

All study-related documents must be retained for the maximum period required by applicable federal regulations and guidelines or institutional policies.

CONFIDENTIAL

This document is confidential. Do not disclose or use except as authorized.

13.6 Multi-center Guidelines

N/A

13.7 Cooperative Research and Development Agreement (CRADA)/Clinical Trials Agreement (CTA)

[figure not shown]
N/A

14. STATISTICAL CONSIDERATIONS

14.1 Study Design/Endpoints

We will have two groups of patients, those treated with radiation alone, and combination of surgery and radiation. Figure 13 summarizes the proposed enrollment groups for this study, depending on the type of treatment patients are undergoing.

Figure 13: Proposed Subject Enrollment Plan

14.1.1 Primary Endpoint

- *Outcome of interest:* change in trabecular bone mineral density (Tb. BMD) measured by QCT of the lumbar spine at the start and at the end of radiation treatment

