1.2 Primary Objectives

- 1.2.1 To measure the effect of high doses of radiation on trabecular bone mineral density (Tb. TBD) in the adult sacrum using the quantitative computer tomography technique (QCT) in patients undergoing treatment with combination surgery and adjuvant radiotherapy, or radiation alone.

CONFIDENTIAL

This document is confidential. Do not disclose or use except as authorized.

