2. BACKGROUND

2.1 Rationale

[figure not shown]
External beam radiation plays an important role in the management of bone malignancies. In combination with surgical resection, high dose radiation was shown to significantly improve survival in historically difficult to treat tumors [4, 6, 15, 22]. The detrimental effects of radiation increase proportionally with the dose delivered. Even at relatively low doses of radiation (30 to 40 Gy), skeletal complications such as radiation-induced osteoporosis, insufficiency fractures (see

Figure 3), physeal arrest, and non-union are common [2, 14, 21, 29, 33]. At high doses (70 Gy and above), the rate of bone-related complications increases dramatically. Despite the high rate of complications, high-dose radiation is becoming increasingly more utilized because of its positive effects on patient survival and prevention of recurrence. For example, combination of surgery and adjuvant radiation doses of greater than 70 Gy achieves meaningful control of locally aggressive tumors (like sacral chordomas), that otherwise have a very high rate of recurrence [6].

CONFIDENTIAL

This document is confidential. Do not disclose or use except as authorized.

Figure 3: Bilateral Sacral Fractures

Given its growing significance in the treatment of malignant bone tumors, we propose to investigate the impact of high dose radiation (over 70 Gy) on human bone metabolism, architecture, and mechanical properties. It is presently unknown what biological mechanisms and structural changes occur in human bone in response to high doses of radiation. Local effects on bone may differ for different parts of the body. To minimize the variability in bone properties, we have chosen to focus this study on one type of bone - the sacrum. Still, our results are likely to be generalizable to other bones because of the common physiology. Sacrum is a particularly good target for this study because 1) tumors affecting the sacrum are often treated with high doses of radiation and 2) sacrum is one of the bones maximally affected by post-radiation complications.

Figure 3 shows a schematic representation of a typical insufficiency fracture that can occur in the sacrum after radiation treatment. Our group recently reported the rate of sacral insufficiency fractures as high as 64% in patients treated with high dose radiation and surgery (submitted). Thus, for the purposes of this pilot study we will focus on patients with primary malignant tumors of the sacrum.

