5. TREATMENT PLAN

CONFIDENTIAL

This document is confidential. Do not disclose or use except as authorized.

Study participants will receive treatment as determined by their treating physicians at the Massachusetts General Hospital for Malignant Bone Tumors of the Sacrum. This may be radiation alone or pre-operative radiation therapy followed by surgery. The treatment plan including MRI and CT imaging is determined by the clinical situation and not by the study. Patients planned for surgery typically receive pre-operative MRI of their pelvis and/or sacrum. In addition, patients often receive a pelvic or sacral computed tomographic image. A CT of the chest is performed to evaluate for pulmonary metastasis. Figure 9 outlines the current standard radiation treatment options. Study participants may also receive radiation therapy as part of another clinical trial. For surgical candidates, the standard treatment includes pre-operative radiation of 50.4 Gy, followed by a recovery period of approximately 4 to 5 weeks. Surgery involves removing the malignant tumor in the sacrum in one piece, preferably with a cuff of normal tissue around the tumor. After approximately 6 weeks of recovery, to allow the surgical incision to heal, the patient is treated with another 19.8 Gy up to 27 Gy of radiation postoperatively depending on the final margin status (higher for gross residual disease), as outlined in Figure 9(A). If the wound is not healed or there is another medical reason to delay adjuvant radiation, then radiation may begin later. The patients are typically followed every 3 months with an MRI of the pelvis/sacrum to evaluate for a local recurrence. A CT scan is often ordered if there is a concern for a fracture. In addition, patients typically receive a chest x-ray at 3 months and 9 months after surgery. A chest CT is ordered at 6 months and 12 months after surgery. The same protocol is used during the second year of follow up. Non-surgical candidates receive 72 up to 77.4 Gy of radiation depending on the histology (72 Gy for osteosarcoma and chondrosarcoma and 77.4 Gy for chordoma) as outlined in Figure 9 (B).

Figure 9: Radiation Treatment Flowchart

CONFIDENTIAL

This document is confidential. Do not disclose or use except as authorized.

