Will perform a volumetric dual energy CT of L1, L2, and S1 using a second-generation dual-source 128-row multi-detector CT scanner (Somatom Definition Flash; Siemens Medical Solutions, Forchheim, Germany). Subjects will be positioned on a quantitative CTPRO calibration phantom (Mindways Software). Helical scans will be performed at 80 and 140 kV by using 210 and 80 mAs, respectively. Other scanning parameters included 1-second gantry rotation time, 0.9:1 pitch, and 64 x 0.6-mm detector configuration with double z-sampling. The images will be reconstructed at 2-mm section thickness and 2-mm section interval by using the I31f reconstruction kernel with a sinogram-affirmed iterative reconstruction (SAFIRE; Siemens Healthcare) setting of 2. The effective dose for each DECT scan is about 2 mSv. For 2 scans, the total effective dose is about 4 mSv which is about the annual background radiation dose.

6.2 **Toxicity Management**

6.2.1 *Management of Tetracycline Toxicity*

Renal / Hepatic Impairment: Tetracycline will not be administered to patients with pre-existing renal or hepatic impairment.

Photosensitivity: Patients will be advised to use skin protection while taking tetracycline. In addition, patients will be advised against prolonged exposure to sunlight and use of tanning equipment. If skin erythema occurs, patients will be advised to discontinue taking the drug and contact the study team.

Superinfection: Patients will be informed of this risk, and will be closely monitored for any GI symptoms. Patients will be advised to discontinue taking the drug and contact their primary care provider and the study team, if any symptoms of infection occur.

Pseudotumor: Patients will be advised to discontinue taking the drug and contact the study team if headache, photophobia, gait disturbances, or any other neurological deficits occur.

Special populations: pregnant and lactating women and children will be excluded from the study due to the concerns related to tetracycline use in these populations (outlined in Section 6.1.1 Adverse Effects of Tetracycline 6.1.2).

CONFIDENTIAL

This document is confidential. Do not disclose or use except as authorized.

6.2.2 *Management of Demeclocycline Toxicity*

Diabetes Insipidus: Patients will be advised to discontinue taking demeclocycline and contact their PCP and the study team, if they experience excessive thirst, urination, headache, dizziness, nausea/vomiting, or any other concerning symptoms.

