8. CORRELATIVE/SPECIAL STUDIES

8.1 **Pharmacokinetic Studies**

N/A

8.2 **Pharmacodynamic Studies**

N/A

8.3 **Special Studies**

8.3.1 *Blood Draws*

We will follow the trends in serological markers over a 6 month period beginning prior to the first dose or radiation received by the patient. The study Schema outlines specific time points when we plan to draw

CONFIDENTIAL

This document is confidential. Do not disclose or use except as authorized.

the blood samples. After all studies have been performed we will label the samples with a code. The key to the code will connect the sample with the subjects health information. The key to the code will be kept in a password protected computer of the principal investigator. Samples will be stored at the BioBank and Research Laboratory Services for the Maine Medical Center Research Institute.

Figure 10

What is measured:

- N-Telopeptide (NTX)
- Serum tartrate-resistant acid phosphatase 5b (TRAP5b)
- Osteocalcin (OC)
- Type 1 procollagen N-terminal (P1NP).
- PTH
- Calcium as part of a standard metabolic panel
- Phosphate

8.3.2 *Quantitative CT Scans*

Patients in both arms of the study will undergo two QCT scans. First QCT will be done at Day 1, prior to initiation of radiation treatment. Patients in the Non-Surgical Arm will undergo a second QCT at six months after their first radiation treatment. In contrast, patients in the Surgical Arm will undergo their second QCT immediately prior to surgery, 10 weeks after the first scan. Once the spinal instrumentation is introduced during the surgery, it renders the analysis impossible due to artifact. Scans will be performed by the MGH Musculoskeletal Imaging Research Core (MIRC) under the direction of [name] (Radiology). We will use the QCT Pro protocol, detailed in Section 6.1.3 – Radiation Exposure Risks. Volumetric QCT of L1, L2 and S1 vertebrae will be obtained. Images will be saved in standard DICOM format and transferred to a PACS workstation for analysis.

What is measured:

- Trabecular bone mineral density (Tb. BMD)

8.3.3 *Bone Biopsies*

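### The primary endpoint (14.1.1) names the lumbar spine while the primary objective (1.2.1) names the sacrum, and its end-of-radiation timing does not match the scan plan

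*Combined protocol and SAP*

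**What the plan says.** **Site.** Primary objective 1.2.1 places the measurement "in the adult sacrum using the quantitative computer tomography technique (QCT"). Section 2.1 gives the reason for a single site: "we have chosen to focus this study on one type of bone - the sacrum". Section 14.1.1 instead defines the primary outcome as the change in trabecular BMD "measured by QCT of the lumbar spine at the start and at the end of radiation treatment".

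**What is scanned.** Section 8.3.2 says "Volumetric QCT of L1, L2 and S1 vertebrae will be obtained", and Section 6.1.3 agrees: "Will perform a volumetric dual energy CT of L1, L2, and S1". Section 8.3.2 lists trabecular BMD as the quantity measured, with no site attached.

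**When.** Both arms have a first scan before radiation starts. For the second, Section 8.3.2 says "patients in the Surgical Arm will undergo their second QCT immediately prior to surgery, 10 weeks after the first scan", and for the other arm "Patients in the Non-Surgical Arm will undergo a second QCT at six months after their first radiation treatment". Calendar 9.1.1 puts the non-surgical second scan at Visit 5, about three months after radiotherapy. Section 5 says that after surgery "the patient is treated with another 19.8 Gy up to 27 Gy of radiation postoperatively", depending on margin status.

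**The concern.** The objective and the endpoint are the two places where the protocol fixes its primary variable, and they name different bones. Both regions are imaged, so the data for either reading will exist and nothing in the scan procedure forces the choice. Followed as written, 14.1.1 produces a lumbar result for a study whose stated question is sacral. Section 14.2 says the pilot is partly meant to supply numbers for later studies. A lumbar mean change and SD would not be the sacral figures that those studies would need.

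The time in the same sentence is also unreliable. It describes one common point, the end of radiation, whereas the scan plan has a different second-scan time in each arm and two different times for the non-surgical arm.

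**Working it through.** **1. The plan's own figures.** Section 14.2 assumes a mean change of 10 mg/mL and an SD of the change of 15 (printed as mg/dL; the figures reproduce when it is read as mg/mL), with alpha 0.05. For a two-sided paired t-test, power comes from the noncentral t with n − 1 degrees of freedom and noncentrality (10/15) × √n.

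| n | Noncentrality | Power computed | Power stated |
|---|---|---|---|
| 30 | 3.65 | 0.9416 | 0.942 |
| 20 | 2.98 | 0.8073 | 0.807 |
| 10 | 2.11 | 0.4692 | 0.469 |

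All three reproduce. The calculation does not depend on which bone is meant, so it neither causes nor settles the conflict.

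**2. Does any other text settle the site?**

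| Place | What it gives | Names a primary site? |
|---|---|---|
| 1.2.1 | Sacrum | Yes, sacrum |
| 14.1.1 | Lumbar spine | Yes, lumbar |
| 2.1 | Study focus on the sacrum | Intent only |
| 2.4.2 | Regions of interest at L4, sacral alae and midline S1 | No; L4 is not a scanned level |
| 6.1.3, 8.3.2 | L1, L2 and S1 scanned | No |
| 14.2, sample size | Lumbar reference density; baseline lowered partly for sacral tumors; change of 10 and SD of 15 without a site | No |
| 14.2, analysis | Radiation effect tested by comparing iliac crest with sacrum | No; these are the biopsy sites in 8.3.3, and the iliac crest is not a QCT level |

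Only 1.2.1 and 14.1.1 name a site for the primary measurement, and they disagree.

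**3. Surgical arm timing.** Preoperative radiation is 50.4 Gy and postoperative radiation is 19.8 to 27 Gy (Section 5).
- Lower planned total: 50.4 + 19.8 = 70.2 Gy; 50.4/70.2 = 0.718.
- Upper planned total: 50.4 + 27 = 77.4 Gy; 50.4/77.4 = 0.651.

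The second scan therefore follows about 72% to 65% of the planned dose. Calendar 9.1.2 ends preoperative radiation at about 5.5 weeks, and 8.3.2 puts the scan at 10 weeks. Even measured from the end of preoperative radiation, the scan is about 10 − 5.5 = 4.5 weeks later.

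**4. Non-surgical arm timing.** The course lasts 7 to 8.5 weeks (Section 2.1). Three months is taken as 13 weeks and six months as 26.
- Calendar 9.1.1: 7 + 13 = 20 weeks to 8.5 + 13 = 21.5 weeks after the start of radiation.
- Section 8.3.2: 26 weeks after the start.
- Gap: 26 − 21.5 = 4.5 weeks to 26 − 20 = 6 weeks.

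Neither time is the end of radiation. The calendar places the scan about 13 weeks after it; Section 8.3.2 places it 26 − 8.5 = 17.5 to 26 − 7 = 19 weeks after it.

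**The case against.** The best defence is that 14.1.1 contains a drafting slip. The protocol uses the term loosely: 2.4.2 describes lumbosacral regions of interest, including the alae and S1, yet the figure it cites is titled as lumbar. With 1.2.1 and 2.1 plainly sacral, most readers would guess the intent. This is probably right, but it supports correcting the sentence. No text says that lumbar stands for S1, or that L1/L2 was meant as a control.

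On timing, calendar 9.1.2 labels the end of preoperative radiation separately from the end of postoperative radiation, so 14.1.1 could mean the former in the surgical arm. Section 8.3.2 also explains why the scan must precede surgery: the instrumentation makes later analysis impossible. That explanation stands, and nothing here suggests moving the scan. The endpoint wording still fits neither arm. The calendar times are approximate and move with treatment, so the 4.5 to 6 week gap is approximate too.

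Several figures and the study schema cited in 8.3.1 are not visible in the text available. The absence of a reconciling statement is therefore a finding about the text shown.

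Three stronger readings are tempting, and the documents do not support them:
- **That the site would be picked after the results are seen, inflating the false-positive rate.** The wording leaves the choice open, but no passage describes such a procedure, so no error rate can be attached to it.
- **That power falls short because some patients will lack a usable S1 region.** No evaluability rate is given, and loss of patients would affect a lumbar endpoint in the same way.
- **That a lumbar endpoint would miss the effect by a known amount.** No expected change or SD is given by site.

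**Conclusion.** The point holds as an internal contradiction in the definition of the primary endpoint, and it should be corrected before analysis. As written, 14.1.1 yields a lumbar result that does not answer objective 1.2.1. Its timing matches neither arm's second scan: the surgical scan follows about 72% to 65% of the planned dose, and the non-surgical scan has two stated times roughly 4.5 to 6 weeks apart.

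The dose shares rest on the totals in Section 5, and the gap rests on 13-week and 26-week conversions. The consequence for the estimate cannot be quantified from the documents. The stated power of 0.942, 0.807 and 0.469 is correct for its assumptions. Choosing S1 as the primary site follows from 1.2.1 and 2.1; keeping the lumbar spine would mean rewriting 1.2.1 and would go against the rationale.

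**What to change.** 1. **Section 14.1.1, site.** Replace the lumbar spine with the within-patient change in sacral (S1) trabecular BMD as the single primary measure. Name the region of interest before data are seen: midline S1, the alae, or a stated combination. S1 alone is not specific enough, because 2.4.2 lists midline S1 and the alae separately. Make the L1/L2 change secondary.
2. **Section 14.1.1, time.** Replace the end-of-radiation wording with the actual scan times by arm, and note that the surgical second scan reflects preoperative radiation only.
3. **Sections 8.3.2 and 9.1.1.** Reconcile them to one non-surgical second-scan time.
4. **Section 14.2.** State that the reference density is lumbar and that the change of 10 and the SD of 15 are not site-specific data.
5. **Unusable S1 regions.** Report how many patients lack one and why, and do not substitute L1/L2 values. Do not simply adopt a rule that drops these patients from the primary analysis. Section 2.4.2 says regions avoid fracture sclerosis and also that radiation causes trabecular sclerosis, so such a rule could remove the most affected patients.

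The cost is protocol wording only. S1 is already included in both scans, so no extra scan, visit or patient is needed.
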